#### *Collected directly by study through questionnaire for VOT/DOT observer at 2 and 6 months:*

- Time spent observing each dose over the previous week (including travel time where relevant) – staff band and employer
- Time spent re-engaging patients with DOT/VOT
- Travel costs to meet with patients for re-engagement
- Any major side effects requiring a change in treatment regime

*Collected by treating clinic* - Sputum culture at 2 months after start of treatment. If required, additional testing will be performed until conversion.

*Collected from national surveillance data*

- Treatment outcome at 12 months (Completed, loss to follow up, transferred out, died)
- Acquisition of new resistance
- Membership of a transmission cluster (based on data from national strain typing service)

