### **11a) Interventions for each group**

VOT: Daily submission of VOT clip using dedicated smartphone with pre-loaded app allowing upload to a secure server. Participants will be trained on how to lay out each drug on a labelled laminated medication sheet with a space for each drug and take each drug type individually saying either the name of the drug or the colour of the pills, size, and the number taken. Participants will be asked to show their mouth is empty by opening their mouth and sticking out their tongue and finally be asked to report any symptoms from a list of key side effects (which will be printed on the reverse of the laminated medication sheet – **Appendix 1 & 2**). Any reported or observed side effects will be addressed by study nurses as indicated in **Appendix 3**.

Training will include submission of test videos.

VOT clips will be submitted automatically as soon as the phone is connected to a cellular data network (data plan provided with phone) or wireless network.

VOT clips will be read by a study nurse/VOT observer daily during weekdays with weekend clips read on Mondays.

No incentives or travel costs will be provided but participants will be able to make use of study smartphone for e-mails, domestic telephone calls and internet searches (limited data downloads apply).

After any missed dose of VOT the observer will attempt to contact the patient by telephone to find out what the problem is and encourage submission of further video clips. If this is a technical problem that cannot be resolved over the phone a visit will be arranged to resolve this. If they are unable to contact them within 24 hours of a missed dose they will contact the case manager to discuss.

DOT: A trained health professional, or responsible lay person supported by a trained health professional, provides the prescribed medication and observes the patient swallowing every tablet prescribed (or for some schedules observing doses during weekdays with self-administered therapy at weekends). Organised by clinic according to usual practice – may be

- a) clinic based
- b) community based working with a responsible professional such as a hostel worker or pharmacist
- c) through a DOT worker outreaching DOT.

Clinics may choose to use incentives and provide travel costs as per normal practice

After each missed dose of DOT the case manager will attempt to contact the patient by telephone to find out what the problem is and encourage re-engagement.

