### *Secondary Outcome measures:*

#### *Collected continuously:*

- Proportion of doses observed over 2 months (continuous variable – comparison of means)
- Proportion of doses observed over 6 months (continuous variable – comparison of means)
- Reported side effects

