## **Methods: Data collection, management, and analysis**

### **18a) Data collection methods**

Recruitment data (CRF 1 - Appendix 7): Recruiting clinics will collect anonymous data on the characteristics of patients who were approached for the trial but declined to participate using a study recruitment log sheet. This will include age, sex and factors that make them eligible for DOT.

Baseline Data (CRF 2 – Appendix 8): Study or clinic nurses will collect baseline data at the time of initial recruitment. This mainly consists of data already routinely collected by clinics, covering patient demographics, disease categorisation and factors that make them eligible for DOT. It will also include the validated EQ-5D quality of life scale and information on employment status and approximate weekly salary

VOT/DOT diary (CRF 3 – Appendix 9):

This will be recorded by the DOT observer at the time of the scheduled session and by the VOT observer at the time of reading scheduled video clips. DOT/VOT observers will be trained to complete (CRF 3 – see section 18a) consistently. CRF3 will be faxed/emailed on a weekly basis to the study centre with the study centre following up with DOT observers when weekly forms are not returned. CRF3 will be completed directly at the study centre on the VOT reading system.

The VOT reading system includes: fields to identify when doses are scheduled; when clips are submitted and read and the following categorisation of clips:

Patient took meds?

- Y (Yes, all meds)
- P (Probably)
- S (Yes, some meds)
- N (No meds taken)
- U (Unable to tell)
- DNA / Did not send clip

This data will be used for the primary outcome and secondary adherence outcome measures.

The system also collects additional data on video and audio quality. The system collects data on geo-location at the time of recording. This will be collected if the participant provides separate consent for this.

DOT: A DOT diary will be completed by DOT observers showing when doses are scheduled to be observed, whether or not the participant attended, when they attended and whether they took the medicines categorised as above.

Patient 2 and 6 month follow up (CRF 4a & 4b – Appendix 10): The study team will contact the participant by telephone to complete a 5 minute questionnaire covering

- Quality of Life (EQ5D)
- Participant satisfaction (Likert scale)
- Participant resource use for DOT/VOT (Participant time, missed work)
- Employment
- Hospitalisation

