VOT/DOT observer 2 and 6 month follow up (CRF 5a & 5b – Appendix 11): This will be completed by the VOT/DOT observer and contain the following information.

- Time spent on average observing doses over 2 or 4 month period (including travel time where relevant) – staff band and employer.
- Time spent re-engaging patients with DOT/VOT.
- Travel costs to meet with patients for re-engagement

sputum sample: At the outpatient appointment closest to 2 months after randomisation the clinic nurse will request a sputum sample and submit this to the local microbiology laboratory for smear and culture.

End of VOT/DOT participant engagement (CRF 6 – Appendix 12):

Semi-structured interviews will be performed with a purposively sampled subset of DOT and VOT participants to understand issues related to provision of DOT/VOT.

12 month follow up (CRF 7 – Appendix 13): The study data manager will work with PHE to link the participant register with national surveillance data to ascertain the following routinely recorded variables.

- Treatment outcome at 12 months (Completed, loss to follow up, transferred out, died)
- Acquisition of new resistance
- Membership of a transmission cluster (based on data from national strain typing service recorded in Enhanced surveillance)

Processes to promote data quality include:

- Training of study and clinic nurses
- Training of DOT and VOT providers
- Weekly submission of DOT diaries + Weekly VOT summary report
- Chase up of DOT provider if weekly forms not submitted
- Quality control visits to clinics every 3 months
- Double data entry for all paper-based CRFs

**18b Plans to promote participant retention and complete follow-up, including list of any outcome data to be collected for participants who discontinue or deviate from intervention protocols**

The study is predicated on maintaining regular contact with participants to monitor adherence.

Participants who are lost to follow up but have not withdrawn from the study, scheduled observations after loss to follow up will be recorded as not having been completed. It will also remain possible to obtain their final outcome data from national tuberculosis surveillance. For participants in the DOT arm who clinics decide to step-down care from DOT to self-administered therapy data will be collected on outpatient clinic attendance and collection of medications.

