## **Statistical methods**

### **20a) Statistical methods for analysing primary and secondary outcomes.**

Characteristics of those randomised and those not randomised due to refusal or exclusion criteria will be compared. Baseline characteristics of those randomised to intervention and control arms will be compared to check for balanced randomisation. An intention to treat analyses will be used. Categorical outcomes will be compared across groups using the chi-square test or Fisher's exact test as appropriate. Continuous variables will be compared across groups using the Wilcoxon rank-sum test.

For some DOT schedules weekend doses are planned to be self-observed due to difficulty in providing DOT at the weekend. For the primary outcome these doses will not be considered in the denominator of scheduled doses, however, as this is a valuable advantage of VOT, secondary analyses will include these weekend doses as part of the treatment schedule). When participants are in hospital their dose will be considered to have been observed. When participants are in prison or custody the dose will be considered to have been observed if it can be verified with offender health that they were aware of the treatment regime. When patients are out of the country VOT participants will be encouraged to continue to take VOT clips which can either be submitted via a wifi connection or will automatically submit on return to the UK. Doses due during time abroad will not be considered as part of the primary outcome for either arm, but will be included in the secondary analyses to explore the potential value.

Patients who cross-over trial arms (see section 11b) prior to the end of 2 month follow up will be considered a failure for the primary outcome.

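### Major side effects are assigned to an observer form whose described contents omit them, and the continuously reported side effects are prompted from a list only in the VOT arm as described

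*Protocol*

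**What the plan says.** Section 12 of the protocol names two side-effect outcomes. Under the continuously collected secondary outcomes it lists "Reported side effects", with no restriction to one arm. Under the observer questionnaire at 2 and 6 months it lists four items, the last being "Any major side effects requiring a change in treatment regime".

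Section 18a then describes that questionnaire (CRF 5a and 5b, Appendix 11): "This will be completed by the VOT/DOT observer and contain the following information". Three items follow: time spent observing doses, time spent re-engaging patients, and travel costs for re-engagement.

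On how symptoms are elicited, section 11a specifies for VOT "Daily submission of VOT clip using dedicated smartphone with pre-loaded app" and says that participants will "finally be asked to report any symptoms from a list of key side effects", which is printed on the back of the medication sheet. For DOT, the same section says a professional or supported lay person "provides the prescribed medication and observes the patient swallowing every tablet prescribed". It mentions no symptom question. Section 18a describes the DOT diary (part of CRF 3) as showing scheduled doses and "whether or not the participant attended, when they attended and whether they took the medicines categorised as above".

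Section 20a gives the general analysis rule: "Categorical outcomes will be compared across groups using the chi-square test" or Fisher's exact test. The timeline in section 13 states that side effects are monitored during months 0 to 2 of DOT or VOT, without naming a form or a method.

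**The concern.** There are two linked problems. First, sections 12 and 18a disagree about whether the observer form collects major side effects. If the form is built from section 18a, that outcome has no described source, and an analysis plan cannot recover data that were never collected.

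Second, the remaining side-effect outcome is elicited differently by arm. A participant asked about a symptom list every day is likely to report more than one who is not asked, whatever the true frequency. Allocation cannot be masked from participants or care providers (section 17a), so nothing in the design offsets this. If the general test is applied, equal tolerability could be reported as an excess of side effects under VOT, and a real difference in either direction would be hard to interpret.

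**Working it through.** **Step 1. The observer form in its two descriptions.**

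| Item | Section 12 | Section 18a (CRF 5a/5b) |
|---|---|---|
| Time observing doses | yes | yes |
| Time re-engaging patients | yes | yes |
| Travel costs for re-engagement | yes | yes |
| Major side effects leading to a regimen change | yes | not listed |

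The participant interview (CRF 4a/4b) does not fill the gap. Its listed topics in sections 12 and 18a are quality of life, satisfaction, resource use, employment and hospitalisation.

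**Step 2. Elicitation and recording of continuously reported side effects, as described.**

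| | VOT | DOT |
|---|---|---|
| Prompt | printed symptom list at each daily clip (11a) | none described |
| Record (CRF 3, 18a) | schedule, clip and intake fields, video and audio quality, geo-location; no side-effect field described | schedule, attendance, time, intake; no side-effect field described |
| Monitoring stated (13) | yes | yes, method not given |

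The difference that the text supports is in prompting. Neither arm has a described field in which to record the answer.

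**Step 3. How large could the effect be?** The protocol gives no side-effect rate and no capture rate, so there is no plan figure to reproduce. What follows is an illustration.

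Inputs: 200 per arm (section 14: 400 in total, 1:1); two-sided 5% level (section 14). Assumptions: true proportion with a side effect 30% in both arms; VOT captures all of them; DOT captures a fraction c; no switching between arms.

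Observed proportions: p1 = 0.30 and p2 = 0.30c. With p̄ = (p1 + p2)/2 and n = 200:

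- SE0 = √[2p̄(1 − p̄)/n]
- SE1 = √[(p1(1 − p1) + p2(1 − p2))/n]
- P(significant) = Φ[(p1 − p2 − 1.96·SE0)/SE1]

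| c | p1 v p2 | SE0 | SE1 | Argument of Φ | P(significant) |
|---|---|---|---|---|---|
| 50% | 30% v 15% | 0.0418 | 0.0411 | 1.66 | 95% |
| 60% | 30% v 18% | 0.0427 | 0.0423 | 0.86 | 80% |
| 80% | 30% v 24% | 0.0444 | 0.0443 | −0.61 | 27% |

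**Step 4. Sensitivity to the assumptions.** Full VOT capture is generous. With 90% VOT capture and true rates from 10% to 40%, the same formula gives:

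- DOT capture 70% (apparent risk ratio 0.9/0.7 = 1.29): 11% to 40%
- DOT capture 50% (apparent risk ratio 0.9/0.5 = 1.80): 35% to 95%

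The size depends heavily on the assumed rates. The direction does not, provided that prompting raises reporting.

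**The case against.** The strongest reply is that the forms themselves (Appendices 9 and 11) are not shown and may contain the items. Section 18a does not present its account of the diary as exhaustive, and section 13 shows that monitoring is intended in both arms. This stands as a limit. A reader might infer that the DOT diary definitely lacks a side-effect item, but the documents support only that none is described. If the forms do carry the item, section 18a still has to be brought into line with section 12.

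A reader might also infer that recording is deficient only in DOT. That is not supported: the VOT reading system as described has no side-effect field either. Nor is the observer form the only instrument that could treat the arms alike. CRF 3 and CRF 4a/4b also serve both arms.

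It can further be said that no sentence specifically commits the trial to testing side effects between arms, that side effects are not among the stated objectives, and that an analysis plan could choose to describe them only. It is true that the comparison follows from the outcome list and the general rule in section 20a taken together. But section 20a makes no exception for side effects, so following the protocol as written leads to the test.

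Finally, DOT is organised according to each clinic's usual practice. Adding a symptom list to every session would alter the comparator slightly. This stands, and it bears on the choice of fix.

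**Conclusion.** The point holds as a contradiction between sections 12 and 18a on the contents of the observer form, together with unequal prompting for the continuously reported outcome. A between-arm comparison of reported side effects could be confounded by prompting, with VOT looking worse.

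It would go too far to say that the comparison would measure prompting instead of toxicity, or that a false finding is to be expected. The 95% to 27% range rests on an assumed 30% true rate, full VOT capture and 50% to 80% DOT capture, none of which comes from the documents. Less extreme assumptions give figures as low as 11%.

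A secondary safety outcome is affected. The primary outcome and the sample size are not. The change should be made, because the outcome cannot be read safely as planned and the correction is small.

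**What to change.** 1. Reconcile sections 12 and 18a: list major side effects leading to a change of regimen among the contents of CRF 5a/5b, for both arms, and check that Appendix 11 carries the item.
2. Base the between-arm comparison of side effects on that item. It is asked of observers in both arms at the same times, and a change of regimen depends less on prompting than a reported symptom does. It is not wholly immune, since observers know the allocation.
3. In section 20a, exempt continuously reported side effects from the general test. Report them descriptively by arm, with a note that VOT participants were prompted from a list and that no equivalent prompt is described for DOT.
4. Optional: record the same symptom item on CRF 3 in both arms.

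The first three changes cost one line on a form already completed in both arms and two short text edits. The fourth adds work for DOT observers and slightly changes the usual-practice comparator, so it is not needed to resolve the point.

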**Additional Objectives**

- To measure the impact on adherence over 6 months
- To measure impact on loss to follow up and treatment completion
- To measure effect on culture conversion and development of resistance
- To measure impact on transmission
- To measure impact on quality of life and patient satisfaction
- To assess cost effectiveness of VOT

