Day zero. Time 0-5 mins – Clinic nurse discusses the recommendation that the patient be treated with DOT and the possibility of being involved in a study of how best to observe treatment (face to face) or using video observed therapy. (A, B, C)

Day zero – Time 5-25 minutes - Clinic nurse provides patient information sheet to patient and allows them to assess whether they wish to receive further information. (A, B, C)

Day zero – Time 25-50 minutes –Clinic nurse (A) or study nurse (B or C) explain the study, seek written consent, randomise and arrange onward care.

Day zero – Time 50-60 minutes - study nurse (A) or clinic nurse (B, C) collect baseline data largely populated from existing clinical data/care records.

Day zero Time 60 minutes -120 minutes (A & B) – Training in use of VOT and provision of smart phone.

Day one (or first working day after day zero) – (C) VOT training up to 1 hour at patients home or at clinic depending on patient preference.

Day one (A & B) or two (C) – VOT arm – patient attempt to submit VOT clip unaided, study team liaises and arranges further training if necessary.

Day one (or first scheduled DOT appointment) – patient begins attending for DOT.

[figure not shown]
0-2 months – regular DOT/VOT with adherence data collection and monitoring of side effects.

2 months – Study team contact participant by telephone to complete follow up questionnaire covering satisfaction with DOT or VOT, Time spent on DOT or VOT, Employment and quality of life, periods of time spent away from home.

Regular out-patient appointment closest to 2 months clinic nurse requests sputum sample to test for culture conversion at local laboratory.

6 months or end of treatment - Study team contact participant by telephone to complete end of follow up questionnaire covering satisfaction with DOT or VOT, Time spent on DOT or VOT, Employment and quality of life, periods of time spent away from home. For patients still requiring onward care the study will liaise with the clinic and Find&Treat to organise continuing DOT or VOT.

Schematic of participant timeline

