#### **15) Recruitment Strategies for achieving adequate participant enrolment to reach target sample size.**

Recruitment relies on conducting the study in multiple centres. We have focussed recruitment of clinics based on existing good relationships and high numbers of cases eligible for DOT. We are also approaching Birmingham clinics to increase numbers.

Based on the following assumptions we expect to be able to recruit 400 patients over a 2 year period.

Assumptions:

The annual number of eligible patients at each clinic will be similar to the annual number of patients reported to national enhanced surveillance in 2010 and 2011 as having social risk factors (homelessness, problem drug or alcohol use or history of imprisonment) but not on DOT, plus the number of patients already on DOT. This averaged at 420 eligible per annum.

It was also assumed that:

95% of those eligible for DOT are also eligible for the trial

Clinics attempt to recruit 75% of those eligible

2/3 of those who are approached agree to participate (based on pilot data VOT acceptance rates)

Note – As MDRTB patients with twice daily treatment are now not included in the randomisation we have not included MDRTB in the estimates. The true numbers of eligibles will be higher as we have ignored, previous history of TB and history of poor adherence, also this is based on incident eligible cases whereas we will also be recruiting patients who are currently on DOT.

We will initially attend outpatient appointments to induct clinics and promote the trial. We will visit clinics monthly for quality control visits.

Another strategy for achieving good recruitment is an emphasis on recruiting patients on the day the study is first introduced to them. As this is a hard – to – engage group delaying this could lead to substantial drop-out.

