## **Methods: Assignment of interventions (for controlled trials)**

Allocation:

16a) Sequence generation

We will use computer generated randomisation by minimisation to ensure balance across study sites and stage of treatment at which recruitment took place 1) at start of treatment; 2) after start but within first 2 months of treatment; 3) After first 2 months of treatment.

This will ensure that treatments are balanced within the two strata.

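### The culture-conversion outcome has two conflicting time origins, and one of them places the sample before randomisation for every patient enrolled after month 2 of treatment

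*Protocol*

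**What the plan says.** Three places in the protocol time the sputum culture.

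- Section 12 (Outcomes), item collected by the treating clinic: "Sputum culture at 2 months after start of treatment", with further tests if needed until conversion.
- Section 18a (Data collection methods): "At the outpatient appointment closest to 2 months after randomisation the clinic nurse will request a sputum sample".
- Section 13 (Participant timeline): "Regular out-patient appointment closest to 2 months clinic nurse requests sputum sample to test for culture conversion at local laboratory". No origin is named, but day zero on that timeline is the day of eligibility, consent and randomisation.

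Recruitment is not confined to the start of treatment. Section 16a minimises on three stages of treatment at recruitment, the last being "After first 2 months of treatment". Section 15 adds that "we will also be recruiting patients who are currently on DOT". The only limit on late entry is in the exclusion criteria: patients with under two months of treatment left are not eligible. The Additional Objectives include the effect on culture conversion.

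**The concern.** An outcome used to compare randomised arms has to be measured after randomisation. If sites or analysts follow Section 12, part of the trial population contributes a culture result that was settled before allocation. Such results cannot differ systematically by arm, so they pull the comparison towards no difference.

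The conflict also affects conduct. Two current sections give clinics different sampling times for the same patient, so results could be collected on a mixture of time scales. A sample taken at the wrong time cannot be recovered at the analysis stage.

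**Working it through.** The protocol gives no power, expected rate or sample size for the culture outcome, so there is no figure to reproduce. The check is one of timing.

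**Inputs.** Section 12: culture at treatment month 2. Section 18a: culture 2 months after randomisation. Section 16a: entry allowed at the start of treatment, within the first two months, or later. Exclusion criteria: at least 2 months of treatment must remain.

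**Formulas.** Let t be the treatment month at randomisation.

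- Section 12 culture, in months after randomisation: 2 − t.
- Section 18a culture, in months of treatment: 2 + t.
- Gap between the two samples: (2 + t) − 2 = t months.

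| Entry at treatment month t | Section 12 culture relative to randomisation | Section 18a culture, treatment month | Gap (months) |
|---|---|---|---|
| 0 | 2 months after | 2 | 0 |
| 1 | 1 month after | 3 | 1 |
| 2 | same day | 4 | 2 |
| 3 | 1 month before | 5 | 3 |
| 4 | 2 months before | 6 | 4 |

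The definitions coincide only at t = 0. For entry between 0 and 2 months, the Section 12 culture reflects less than two months of the allocated arm. For every t above 2, which is the whole of the third stage, it comes before randomisation.

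**How far before.** Treatment length L is not stated. Since at least 2 months must remain, the latest entry is t = L − 2, and the Section 12 culture then precedes randomisation by t − 2 = L − 4 months. Assuming L = 6, 9 or 12 months gives up to 2, 5 or 8 months.

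**Dilution.** If a share s of the analysed patients has a pre-randomisation culture, and the average difference between arms among the rest is Δ, the pooled difference is (1 − s)Δ. The protocol does not give s or an expected Δ, so the direction is known and the amount is not.

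**Under Section 18a.** No sample predates randomisation. However, a patient entering at month 3 is sampled at month 5 and may have converted before entry. Such a patient contributes nothing to a comparison of conversion. The testing until conversion in Section 12 helps only those who have not yet converted.

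**The case against.** The strongest reply is that Section 18a is the operating instruction and the Section 13 timeline agrees with it. Clinics would then sample from randomisation, and the Section 12 wording would be a slip. This stands in part: pre-randomisation cultures arise only if Section 12 is followed. Even so, Section 12 is where the outcome is defined, and Section 18a alone does not deal with patients who converted before entry.

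A second reply is that allocation is minimised on stage of treatment, residual imbalance is to be adjusted for, and effect modifiers are to be examined by interaction terms. This also stands as far as it goes: neither arm is favoured. Balance between arms does not restore an effect to results fixed before allocation.

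A third is that an analysis plan could settle the matter. It could define the analysis set, but it cannot change when a sample was taken, and the contradiction lies within the protocol.

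A reader might extend the point to the surveillance outcome "Membership of a transmission cluster (based on data from national strain typing service", which serves the objective "To measure impact on transmission". The documents do not support calling this the same flaw. Its two listings do not conflict on timing, and the protocol does not say when the typed isolate is taken or how a cluster is defined. A claim that membership predates randomisation would rest on outside knowledge.

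**Conclusion.** The point holds for culture conversion. The protocol has two incompatible time origins for one secondary outcome, and under Section 12 every patient in the third stage has a 2-month culture that predates randomisation. This follows from the text alone; only the range of up to 2, 5 or 8 months depends on assumed treatment lengths.

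The loss of effect cannot be quantified. A reader might want to turn the dilution into a sample-size multiplier. That would need a share of late entrants that the protocol does not give, and for pre-randomisation cultures it would apply only if Section 12 governs. A reader might also infer that the culture objective goes unanswered. That is too strong, since patients randomised at start of treatment, and in part those enrolled within the first two months, still inform it.

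The primary outcome is timed from randomisation, so it and the sample size are unaffected.

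**What to change.** Reconcile Sections 12, 13 and 18a so that the trial's culture outcome has one origin, randomisation, and name that origin in each place. This concerns the trial outcome only; cultures taken for clinical care remain with the treating clinic.

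Make the main conversion comparison in participants randomised at start of treatment, for whom the two timings already coincide, and report the other two stages separately. Stage at entry is already recorded for minimisation, so no new data are needed. Restricting instead to patients who are culture-positive at entry would be the more direct definition of those at risk. However, the baseline data described in Section 18a do not list culture status at entry, and Section 33 provides for no further specimens, so that route would need an added data item.

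The cost is a wording amendment and a smaller analysis set, hence less precision, for this secondary outcome.
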